10.8.4 Safety Monitoring

According to University of Chicago Cancer Center Guidelines, this protocol will be
Page 40 of 59

classified as moderate risk. Data and Safety Monitoring (DSM) will occur at the weekly University of Chicago Genitourinary Oncology DSM meeting. At each meeting, the study will be reviewed for safety and progress toward completion. Toxicities and adverse events will also be reviewed and a DSM form will be completed at each meeting. Twenty percent of research charts will be audited annually for protocol compliance items including eligibility, completion of procedures, administration of treatment, reporting of toxicities, documentation of response, follow-up, data-collection, record keeping, and the collection of correlative studies. Safety of participating subjects at other sites will also be reviewed at the University of Chicago DSM, however safety will also be monitored locally per each institutions guidelines. During the phase 1 portion of the study, there will be weekly teleconferences between participating centers to review subject safety and study progress. For the phase II portion, there will be a similar monthly teleconference.

10.8.5 Independent Safety Monitor

[name], PhD, Director for Clinical Research Operations in the University of Chicago Comprehensive Cancer Center, will serve as the Independent Research Monitor (IRM) for this study as stipulated by DOD Directive 3216.02. The principle role of the IRM within the context of this study will be to oversee study conduct specifically with respect to safety. Given the phase I/II nature of the study, and the potential for dose adjustments based on both pharmacokinetics and safety, the IRM will have direct oversight with respect to assessment of patient safety, independent of the research team. In the case of serious adverse events or subject deaths that she feels meet the criteria to be classified as unanticipated problems, her independent report in the form of a memo will be promptly submitted to the DOD (USAMRMC ORP HRPO) and University of Chicago IRB along with the report of the event. In addition to attending weekly data safety monitoring meetings, she will participate in the regular teleconferences once more than one site is participating in the trial. In the event that she is not able to attend the data safety monitoring meeting in person, she will review the data safety monitoring minutes from that meeting. Specifically, she will review all unanticipated problems involving risk to subjects or others, serious adverse events and all subject deaths associated with the protocol and provide an unbiased written report of the event should she feel it qualifies as an unanticipated problem. For those events qualifying as unanticipated problems, the IRM will comment on the outcomes of the event or problem and, in case of a serious adverse event or death, she will comment on the relationship to participation in the study. The IRM will indicate whether she concurs with the details of the unanticipated problem report provided by the principal investigator. Reports for events determined by either the investigator or research monitor to be possibly or definitely related to participation and reports of events resulting in death will be promptly forwarded to the USAMRMC ORP HRPO and the University of Chicago IRB. The IRM has the authority to stop this research protocol in progress in parallel with the submission of a UP to the University of Chicago IRB, remove individual human subjects from this research protocol, and take whatever steps are necessary to protect the safety and well-being of human subjects participating in this protocol until the University of Chicago IRB assesses the UP and the IRM's report and determines appropriate next steps.

11.0 MEASUREMENT OF EFFECT

Patients with measurable disease will be assessed by standard criteria^{45,46} (Appendix C, D). For the purposes of this study, patients should be re-evaluated every 12 weeks.

11.1 Outcome Measures based on PSA Decline

The following parameters will be recorded after the initial 12 weeks of therapy and at 12-week intervals thereafter.

- PSA decline and response will be measured according to PSAWG-2 (2008) criteria.
- PSA changes from baseline will be calculated for all patients and reported as a waterfall plot.
- Time to progression (TTP) based on revised PSA Working Group-2 criteria (2008 version).
- PSA progression free survival: PSA measurements will be taken at screening (baseline) and subsequently at time points as indicated in the schedule of visits. Any unscheduled PSA measurement will be utilized in the periodic assessment of PSA progression.
- The maximal decline in PSA for each patient will be recorded for each patient.
- The date of the maximal PSA decline (nadir date) will be recorded for each patient, as will the duration from the start of therapy to the nadir PSA.

11.2 Radiographic Tumor Response

Change in measurable disease, when applicable, will be determined according to RECIST 1.1 and PSAWG-2 criteria (Appendix E)^{45,46,49}. For the purposes of this study, imaging will be repeated according to the study calendar (Section 8.0) every 12 weeks unless otherwise indicated clinically.

Lymph nodes⁴⁶: To be considered pathologically enlarged and measurable, a lymph node must be at least 15 mm in short axis when assessed by CT scan (CT scan slice thickness recommended to be not greater than 5 mm). Lymph nodes that are at least 10 mm but less than 15 mm in short axis may be pathologic and can be considered non-measurable/non-target lesions (that are not measured). At baseline and in follow-up, only the short axis will be measured and followed.

Bone lesions: Bone lesions are by definition non-measurable. If bone lesions are identified on MRI that have soft tissue components that are identifiable and accurately measurable the bi-dimensional measurements of these lesions will be recorded as soft tissue measurable disease. Of note, progression based on bone scan will be assessed according to PSAWG-2 criteria⁴⁹. Isolated new lesions on bone scan at the 12-week scan will be confirmed with a repeat bone scan at 6 weeks to rule out bone scan flair. If no new lesions are seen at the 6-week confirmation, it will be considered flair. All subsequent bone scans will follow standard criteria with regards to progression (two new lesions necessary for progression).

11.3 Duration of Response

The duration of overall response is measured from the time measurement criteria are met for complete or partial response until the first date that recurrent or progressive disease is objectively documented (taking as reference for progressive disease the smallest measurements recorded since the treatment started).

Stable disease is measured from the start of the treatment until the criteria for progression are met, taking as reference the smallest measurements recorded since the treatment started, including the baseline measurements.

11.4 Progression-Free Survival

Progression-free survival (PFS) is defined as the duration of time from start of treatment to time of progression (by either PSA or RECIST) or death, whichever occurs first.

12.0 CORRELATIVE STUDIES

12.1 Circulating Tumor Cells (CTC)

Circulating Tumor Cell isolation and characterization

CTC are emerging potential source of tumor tissue for therapeutic biomarker interrogation. At present, there is no standard procedure for extracting and evaluating CTC beyond enumeration. This study will utilize methodologies developed in the PI's laboratory⁵⁰ for further biomarker validation.

For evaluation of CTC, 15mL of whole blood will be collected in two (7.5mL each) BD CPT vacutainers which will be provided. For this exploratory endpoint, samples will only be collected for University of Chicago study subjects. Samples will be processed within 60minutes of sample acquisition.

CPT tubes will be centrifuged at 1500g for 20minutes at room temperature. Following centrifugation, the uppermost plasma layer will be removed and saved for correlative studies. Mononuclear cell layer will be then transferred from both tubes into one new 15ml conical tube. Phosphate buffered saline (PBS) will be added to a total volume of 15ml. The cells will be centrifuged at 450g for 5 minutes at room temperature. The supernatant will be discarded and the washed mononuclear cells will be resuspended in 10ml of PBS for further processing.

Once mononuclear cell fraction isolated, prostate cancer cells will be identified and further characterized using flow cytometry cell sorting (FACS) and analysis. Pellet of cells will be resuspended in cell separation buffer (PBS with 2mM EDTA, 0.5% serum albumin), FcR blocking buffer (Miltenyi), EpCAM (to bind epithelial cells) and CD45 (to bind white blood cells) primary antibodies conjugated to specific fluorescent markers. Cells will then be analyzed in conjunction with the flow cytometry core facility gating for the EpCAM positive, CD45 negative population. The cells will be characterized using multiplex fluorescent immunocytochemistry with fluorescently conjugated antibodies to the AR, GR (Cell Signaling) along with DAPI nuclear staining.

Cells will be FACS sorted onto charged glass chamber slides, and then fixed with 3% formalin and stained with ICC antibodies for multiplex fluorescence. The slides will be imaged using the Leica SP2 laser confocal microscope. Alternatively, depending on FACS machine availability, the Image Stream flow cytometer may be used to analyze fixed and stained cells. Captured images will be analyzed for fluorescence intensity and digitally scored using ImageJ software. Positive and negative control cells stained concomitantly will also be digitally analyzed and will provide the reference for staining intensity analysis. In

addition to staining intensity, intra-cellular localization will be described for CTC for each marker. Immunofluorescence will be assessed in conjunction with [name] in the Pathology Department, University of Chicago.

12.2 Optional Tumor Biopsies

Studies have shown that GR expression increases in response to androgen pathway inhibition in prostate cancer³². The GR expression in CRPC is unknown. To better understand the potential compensatory role of the GR in CRPC progression, to explore the role of baseline intra-tumoral GR expression as a predictive biomarker for GR inhibition with mifepristone, and to query other resistance pathway mechanisms, subjects will be asked to contribute an optional tumor core needle biopsy (under CT guidance if necessary). An optional biopsy will be obtained both during the screening period and at the off study visit (Section 7.0 above) if possible. While the exact number of specimens obtained depends on the size of the target, the difficulty of the procedure, and risk of complications, the goal is to obtain between 2-3 samples for analysis. A full standard operating procedure (SOP) for biopsy acquisition and handling will be provided to study sites. The primary sample will be fixed in paraformaldehyde, decalcified (if needed) and embedded in formalin. Samples will be processed for immunohistochemistry (IHC) and assessed for standard pathologic parameters (with H&E staining), AR and GR staining. These pathology parameters will be assessed in conjunction with [name] in the Pathology Department, University of Chicago. If a second core biopsy is obtained, it will be embedded in Tissue TekTM OCT and frozen at -80°C for future molecular analysis of AR pathway resistance.

13.0 STATISTICAL CONSIDERATIONS

13.1 Sample Size/Primary Endpoint

Within the phase I portion of the study, steady-state C_{trough} for Enzalutamide and the active metabolite will be determined for each patient and means and standard deviations calculated. As described above, the mean of the ratio of C_{trough} for Enzalutamide and the active metabolite will be calculated for each dosing cohort, and mean value will be used for dos adjustment determinations. Standard deviation and range of the C_{trough} and ratio will also be calculated and reported.

The randomized phase II study, will be conducted with appropriate sample size to power primary endpoint- to determine if mifepristone in combination with enzalutamide prolongs time to PSA progression compared to enzalutamide alone in patients with metastatic castration resistant prostate cancer. The primary statistical consideration will be PSA progression-free survival (PFS) post randomization, defined as the time to PSA progression or death, whichever comes first. PSA progression will be defined as a PSA (confirmed 2 weeks later) that is ≥ 1.25 times (25% increase) the PSA at randomization (week 12). We assume the median time to PSA progression in the control (enzalutamide alone) arm will be 6 months post randomization. The rationale for this assumption is as follows. In the phase III enzalutamide (AFFIRM) trial¹³, ~10% of treated patients had PSA progression prior to 12 weeks. The PSA progression-free rate was ~42% at 9 months, which would correspond to a 6-month rate, conditional on no event at 12 weeks, of $0.42/0.9=0.47$. Thus our enrichment strategy should lead to a patient population with a median PFS of 6 months (24 weeks) in the control arm post randomization. In order to detect a hazard ratio (HR) of 0.60, which corresponds to an increase in the median from 24 to 40 weeks, with 80% power, a sample

size of 84 patients (42/arm) is required, using a one-sided test at the $\alpha=0.10$ significance level. This assumes a two-year accrual period and a subsequent one-year follow-up period. Kaplan-Meier⁴¹ curves will be generated and the two treatment arms compared using a logrank test. Median time to event in each group will be estimated along with 90% confidence intervals using the method of Brookmeyer and Crowley⁴². Cox⁴³ proportional hazards regression models will be fit to assess and adjust for the effects of baseline covariates. Overall survival and radiographic progression-free survival will be analyzed similarly. The relative PSA change within each arm will also be reported using a waterfall plot according to working group recommendations for phase II studies in CRPC, as a secondary endpoint⁴⁴. Adverse events will be summarized by grade and type and compared between groups using chi-square or Fisher's exact tests.

For the secondary endocrine PD endpoint, we will compare endocrine PD marker differences between the enzalutamide alone versus the Enzalutamide + Mif treatment arms. In previous placebo controlled trials of Mif, serum cortisol levels reliably doubled from a baseline of approximately 15 $\mu\text{g}/\text{dL}$ to $>30 \mu\text{g}/\text{dL}$ after treatment with mifepristone^{38,39}. Based on the reported interquartile ranges, and assuming normality of the distribution, the coefficient of variation is estimated at 50%. An interim futility analysis will be conducted after half (35) of the expected 70 PSA events are observed. At this stage we will conduct an interim analysis of the difference in cortisol levels; a lack of biomarker effect would provide justification for closing the trial. Thus, assuming a true mean for the control arm of 15 and standard deviation of 7.5 on day 29 post randomization, our sample size will provide 90% power to detect a difference of 15 vs. 22 $\mu\text{g}/\text{dL}$ between the two treatment arms, based on t-test at a two-sided alpha level of 0.05. This calculation allows for a 15% missing data rate prior to day 29 post randomization. The other endocrine laboratories collected at day 29, will be similarly compared between treatment groups.

In addition, if at the interim analysis the conditional power for the primary PSA endpoint is $<25\%$, we will consider terminating the trial for futility. This stopping rule will provide minimal power loss ($<3\%$)⁴⁴.

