6.0 DURATION OF TREATMENT

Therapy with enzalutamide or enzalutamide/mifepristone will continue until one of the following events occurs.

1. Progression of disease according to 2008 PSAWG-2 criteria⁴⁷ is met (Appendix C, D). Note-PSA progression (or response) will not be assessed until the patients' first 12-week disease assessment visit.
2. Unacceptable toxicity is encountered.
3. Patient withdraws consent
4. Patient is withdrawn from study at the discretion of the investigator

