7.1 Pre-treatment Screening Evaluation

Eligible patients who have signed informed consent and have had eligibility confirmed will be seen in the outpatient clinic within two weeks of starting the study. They will undergo a history and physical examination, have ECOG performance status, concomitant medications, and baseline toxicity documented at this visit. In addition, to confirm eligibility, the patient will have standard of care screening labs drawn within four weeks of initiating therapy. These include: CBC (white blood cell count, hemoglobin, platelet count, white blood cell differential) and serum chemistries (sodium, potassium, chloride, bicarbonate, blood urea nitrogen, creatinine, glucose, calcium, alanine aminotransferase, aspartate aminotransferase, total bilirubin, total protein, alkaline phosphatase, and albumin), LDH, serum testosterone and

PSA. A whole blood sample for circulating tumor cell correlative study will be performed during the screening period and processed as described in Section 12.1. An optional pre-study tumor biopsy will be obtained during screening period (see section 12.2). Subjects will have an EKG to insure normal QTc prior to enrolling.

Disease burden evaluation with a nuclear medicine bone scan (or Fluoride PET), abdominal/pelvis imaging (CT or MRI), and CT chest (when clinically indicated) must be obtained within 30 days of study entry. Study entry date is defined as day of first on-study treatment as detailed in Section 5.1-5.3.

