7.3 Off Study Assessments

Patients will be followed with these assessments until taken off study. Upon study discontinuation, subjects will undergo a complete evaluation with a history and physical examination, ECOG performance status, concomitant medications, and toxicity documented at this visit. The subject will also have standard laboratory studies collected at this visit (CBC, serum chemistries, LDH, PSA, testosterone), and have radiologic tumor assessments performed, unless already performed within four weeks of being taken off study. Study participant refusal or inability to undergo these evaluations should be noted. This visit should be done on the day patients are taken off study medication but may be completed within 30 days of coming off treatment. A third CTC sample will be obtained. In addition, a second optional pre-study tumor biopsy will be obtained at time of disease progression for those coming off study for progression.

[Rest of Page Intentionally Left Blank for Formatting Purposes]

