8.0 STUDY CALENDAR

	Screening ^m	Day1, 15, 29, 43, 57 then Monthly ^g	Every 3Months ^g (beginning at start of concomitant dosing)	Offstudy visit ^j
Procedures				
Informed Consent ^a	X			
Medical History, including demographics	X			
Physical exam, including height (only at screening) and weight	X	X	X	X
Vital Signs ^b	X	X	X	X
ECOG performance status	X	X	X	X
Concomitant medications	X	X	X	X
Adverse Events		X	X	X
EKG	X	X ⁱ		
Laboratory Assessments				
CBC with platelets & Differential counts	X	X	X	X
Serum chemistry and electrolytes ^c	X	X	X	X
LDH	X	X	X	X
PSA	X	X	X	X
Testosterone	X		X	X
Hypothalamic-pituitary labs		X ^k		
PK sample-per Sec. 7.2.1		X ^h		
TumorAssessments^d				
Bonescan/F18 PET ^e	X		X	X
CT or MRI of the abdomen/pelvis	X		X	X
CT chest ^f	X		X	X
Correlative Studies				
Circulating tumor cell (CTC) collection	X	X ⁱ		X
Tumor biopsies (optional)	X			X

- a. Written informed consent must be obtained before any study-specific screening assessments are performed (it can be no more than 28 days prior to starting/beginning study medication).
- b. Includes blood pressure, pulse, respiratory rate, and body temperature.
- c. Serum chemistry includes BUN, creatinine, ALT, AST, glucose, alkaline phosphatase, total bilirubin, electrolytes (K+, Cl-, Na+, CO2, Ca+).
- d. Imaging will be evaluated at screening and for clinical benefit every 12 weeks (3 cycles) of treatment, beginning at start of concomitant drug dosing (day 29 for phase I, day 1 for phase II).
- e. Isolated new lesions on bone scan at the first 12-week scan will be confirmed with a repeat bone scan at 6 weeks to rule out bone scan flair.
- f. Obtain if clinically warranted.
- g. +/- 3 days.
- h. PK assessments per Section 7.2.1(day 29, 43, 57 then monthly)
- i. Whole blood for CTC assessment will be collected on Day 1 of study drug administration.
- j. End of study visit – within 30 days of the last enzalutamide dose. Tumor assessment not necessary if done within preceding 30 days.
- k. Serum TSH and AM cortisol will be measured at day 1, 29, 57

1. EKG to assess QTcon study will be obtained Day 57 for Phase I, Day 29 for Phase II

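### The Section 6 stopping rule can end PSA collection before the Section 13.1 primary event is reached, and Section 13.1 gives no censoring rule for those patients

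*Combined protocol and SAP*

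**What the plan says.** **Primary event (Section 13.1).** PSA progression is a PSA at or above "1.25 times (25% increase) the PSA at randomization (week 12", "confirmed 2 weeks later". The endpoint is the time from randomization to that event or death. The reference is the randomization value, not the nadir.

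**Treatment stop (Section 6.0).** Therapy ends on "Progression of disease according to 2008 PSAWG-2 criteria", as set out in Appendices C and D. The same section adds that "PSA progression (or response) will not be assessed until" the first 12-week disease assessment visit.

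**Appendix C.** After a fall of 50% or more from screening PSA, progression is a 50% rise from nadir with a 5 ng/mL minimum. For smaller falls the appendix gives two rules: 25% above nadir with a rise of at least 5 ng/mL, and, under time to disease progression, 25% above the screening value with no floor.

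**Screening value (Section 7.1).** It comes from "screening labs drawn within four weeks of initiating therapy", so it can differ from the randomization value.

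**End of PSA collection.** Section 7.3 says "Patients will be followed with these assessments until taken off study". The off-study visit, which includes a PSA, "may be completed within 30 days of coming off treatment"; the Section 8.0 calendar puts it "within 30 days of the last enzalutamide dose". The calendar has no later column. Section 11.1 lets unscheduled PSA values count but requires none after this visit.

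**Censoring.** Section 13.1 states no rule for the primary endpoint. Section 13.3, under secondary endpoints, censors PFS at the last tumor assessment. Appendix C censors at the last PSA, but for duration of PSA response.

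**The concern.** Two progression rules with different reference values run in parallel. One decides when a patient stops treatment and leaves scheduled PSA follow-up; the other decides whether he has had a primary event. If the stop comes first, the plan, followed exactly, ceases to look for the event it is meant to count. Radiographic progression does the same by another route: it stops treatment but is not a primary event.

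These patients leave observation when PSA is rising or disease is progressing, so treating them as censored may breach the independence that the Kaplan-Meier, logrank and Cox analyses assume. Each unobserved event also reduces the information in a trial of 84 patients. Without a stated rule, analysts could reasonably build different primary datasets from the same records: censor at the last PSA, censor at the last scan, or count the Appendix C stop as the event.

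**Working it through.** **1. The plan's own figure.** For HR 0.60, one-sided alpha 0.10, 80% power and 1:1 allocation, the Schoenfeld formula gives

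D = [2 × (1.2816 + 0.8416) / |ln 0.60|]² = (4.2464 / 0.5108)² = 69.1, rounded up to 70.

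This matches the 70 expected events in Section 13.1. With exponential medians of 24 and 40 weeks, uniform accrual over 104 weeks and 52 weeks of follow-up, the event probability is 1 − [exp(−52λ) − exp(−156λ)] / (104λ), where λ = ln 2 / median. That gives 0.930 and 0.812, so 42 per arm yield 39.0 + 34.1 = 73.1 events. The sample size arithmetic is sound.

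**2. Which threshold comes first after a fall of 50% or more.** Let S be screening PSA, B randomization PSA and N nadir, in ng/mL. I read the 5 ng/mL minimum as a minimum rise, as elsewhere in Appendix C.

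- Stop: max(1.5N, N + 5)
- Primary event: 1.25B
- The stop is lower when N < 0.833B and N < 1.25B − 5

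| S | B | N | Stop | Event | First reached |
|---|---|---|---|---|---|
| 40 | 40 | 20 | 30 | 50 | Stop |
| 20 | 20 | 6 | 11 | 25 | Stop |
| 40 | 30 | 20 | 30 | 37.5 | Stop |
| 40 | 22 | 20 | 30 | 27.5 | Event |
| 6 | 6 | 3 | 8 | 7.5 | Event |

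The order reverses at low PSA, or when S is well above B. With S = B and fractional fall d, the stop comes first when B > 5/(0.25 + d): 6.7 at d = 50% and 5.3 at d = 70%.

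**3. Falls under 50%.** Both Appendix C rules can stop treatment first.

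- Nadir rule: S = B = 40, N = 24 gives a stop at max(30, 29) = 30 and an event at 50. At low PSA it reverses: S = B = 10, N = 8 gives a stop at 13 and an event at 12.5.
- Screening rule: the stop is 1.25S and the event 1.25B, so the stop is first whenever S < B. With S = 20, B = 24, N = 19, the stop is 25 and the event 30.

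**4. How much 12-weekly assessment recovers.** Sections 11.0 and 11.1 put re-evaluation at 12-week intervals, while PSA is drawn every 2 weeks through week 8 and monthly thereafter (Section 7.2). Suppose 12 weeks pass between reaching the stop threshold and acting on it, and PSA grows exponentially. The gaps in the first two examples are log2(50/30) = 0.737 and log2(25/11) = 1.184 doublings. The event is missed when the doubling time exceeds window / gap:

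- The 2-week confirmation must fall inside the 12 weeks, leaving a 10-week window: 10/0.737 = 13.6 weeks and 10/1.184 = 8.4 weeks.
- The off-study PSA serves as confirmation, so the full 12 weeks are available: 12/0.737 = 16.3 weeks and 12/1.184 = 10.1 weeks.

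These limits treat PSA as continuously observed. Monthly draws, or acting on the stop sooner, would lower them.

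**5. Illustrative cost.** Power = Φ(|ln 0.60| × √D / 2 − 1.2816), with non-informative loss assumed.

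| Events lost (assumed) | Events left of 73.1 | Power |
|---|---|---|
| 0% | 73.1 | 81.7% |
| 10% | 65.8 | 78.5% |
| 20% | 58.5 | 74.9% |
| 30% | 51.2 | 70.7% |

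**The case against.** The best defence is that the plan already limits the problem. PSA progression is not assessed before the first 12-week visit and re-evaluation is 12-weekly, while PSA is drawn more often, so a fast-rising patient can reach 1.25 times the randomization value before anyone acts on the stop. Unscheduled values count, and so does death. This stands in part: step 4 shows recovery for short doubling times. It does not remove the gap for slower risers, nothing requires a PSA after the off-study visit, and if that visit supplies the first qualifying value, no confirming draw is scheduled.

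It can also be said that Section 13.3 speaks of PFS and so covers the primary endpoint. Its heading and its reference to tumor assessments point to the secondary endpoint, so at best the text is ambiguous.

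Excluding radiographic progression from a PSA endpoint is a legitimate choice. The difficulty is only that PSA observation then ends with no stated censoring rule.

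The size of the problem is unknown. The examples need a further fall in PSA in men already up to 12 weeks into enzalutamide, and the documents do not say how often that happens. That objection stands in full.

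A reader might infer that the analysis will favour the combination, because mifepristone could deepen PSA falls and so trigger more nadir-based stops in that arm. The documents do not support this: whether mifepristone affects PSA response is one of the trial's own questions, and no differential loss rate is given. If losses were equal and non-informative, the hazard ratio would be about unchanged and the cost would be power.

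**Conclusion.** The concern holds and should be fixed. The conflict between the thresholds, the end of scheduled PSA collection and the absence of a primary censoring rule are all matters of text. They mean that some primary events can go unobserved, through censoring that is potentially informative.

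The size is not known. The power figures of 78.5 to 70.7% rest on assumed losses of 10 to 30%, exponential event times and non-informative loss; they show sensitivity and do not forecast the trial's power. It would be too strong to conclude that the stop always precedes the event, since the order reverses at low PSA or when screening PSA is well above randomization PSA. It would also be too strong to call the trial underpowered, since the planned 70 events and 84 patients reproduce and no loss rate is documented.

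**What to change.** For phase II, amend Sections 7.3, 8.0 and 13.1 as follows:

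- When treatment stops for any reason other than a confirmed Section 13.1 event, keep recording routine PSA values, including the 2-week confirmation, until the Section 13.1 event, new anticancer therapy, death or data cut-off.
- Censor primary PSA-PFS at the last PSA before new anticancer therapy or data cut-off.

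The cost is protocol wording and a little extra data recording, with no additional patients. Some loss will remain in patients who switch therapy at once, because their later PSA values no longer reflect the randomized treatment.
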